5.2.6.1.4 Adverse events of special interest

The term adverse events of special interest (AESI) relates to any specific AE that has been identified at the project level as being of particular concern for prospective safety monitoring and safety assessment within this trial, e.g. the potential for AEs based on knowledge from other compounds in the same class. AESIs need to be reported to the sponsor's Pharmacovigilance Department within the same timeframe that applies to SAEs, please see Section 5.2.6.1.2.

The following are considered as AESIs:

Inhalation related bronchospasm

Inhalation of the investigational medicinal product may result in airway irritation and/or hypersensitivity that can result in bronchospasm manifesting wheezing, prolonged expiration and respiratory distress.

Hypersensitivity/allergic reaction

Any suspicion of severe infusion reaction and of any potential cases of anaphylaxis should be defined and assessed using the criteria discussed in the statement paper from Sampson HA (Appendix 10.4; R11-4890)

Infusion of biological products including monoclonal antibodies may be associated with the development of infusion related reactions that can occur during and/or within hours of the infusion. Symptoms of infusion related reactions may be related to immediate hypersensivity (allergic reaction, anaphylaxsis) or cytokine-release syndrome. Symptoms of cytokine release syndrome may include, but are not limited to, fever, tachypnea, headache, tachycardia, hypotension, all types of rashes including flushing, and/or hypoxia.

Potential Severe DILI

A potential severe Drug Induced Liver Injury (DILI) that requires follow-up is defined by the following alterations of hepatic laboratory parameters:

- An elevation of AST (Aspartate Aminotransferase) and / or ALT (Alanine Aminotransferase) ≥3-fold ULN combined with an elevation of total bilirubin ≥2-fold ULN measured in the same blood sample, or in samples drawn within 30 days of each other, or
- ALT and / or AST elevations ≥ 10 -fold ULN.

These lab findings constitute a hepatic injury alert and the patients showing these lab abnormalities need to be followed up according to the "DILI checklist" provided in the ISF. In case of clinical symptoms of hepatic injury (icterus, unexplained encephalopathy, unexplained coagulopathy, right upper quadrant abdominal pain, etc.) without lab results (ALT, AST, total bilirubin) available, the investigator should make sure these parameters are analysed, if necessary, in an unscheduled blood test. Should the results meet the criteria of hepatic injury alert, the procedures described in the DILI checklist should be followed.

5.2.6.1.5 Intensity (severity) of AEs

The intensity (severity) of adverse events should be classified and recorded in the CRF according to the DAIDS Table for Grading the Severity of Adult and Pediatric Adverse Events (also known as the DAIDS AE Grading Table; $\underline{R21-0379}$)

For specific events that are not included in the DAIDS AE Grading Table, the generic scale (Table 5.2.6.1.5:1) is to be used:

20 Apr 2021 Page 70 of 127

Proprietary confidential information © 2021 Boehringer Ingelheim International GmbH or one or more of its affiliated companies

Table 5.2.6.1.5:1	Generic AE Grading Scale [R21-0379]
Grade 1	Events causing no or minimal interference with usual social and functional activities, and NOT raising a concern, and NOT requiring a medical intervention/therapy.
Grade 2	Events causing greater than minimal interference with usual social and functional activities; some assistance may be needed; no or minimal medical intervention/therapy required.
Grade 3	Events causing inability to perform usual social and functional activites; some assistance usually required; medical intervention/therapy required.
Grade 4	Events causing inability to perform basic self-care functions; medical or operative intervention indicated to prevent permanent impairment, persistent disability, or death.
Grade 5	Events resulting in death.

5.2.6.1.6 Causal relationship of AEs

Medical judgement should be used to determine the relationship between the adverse event and the BI investigational compund, considering all relevant factors, including pattern of reaction, temporal relationship, de-challenge or re-challenge, confounding factors such as concomitant medication, concomitant diseases and relevant history.

Arguments that may suggest that there is a reasonable possibility of a causal relationship could be:

- The event is consistent with the known pharmacology of the trial drug.
- The event is known to be caused by or attributed to the drug class.
- A plausible time to onset of the event relative to the time of drug exposure.
- Evidence that the event is reproducible when the drug is re-introduced.
- No medically sound alternative aetiologies that could explain the event (e.g. pre-existing or concomitant diseases, or co-medications).
- The event is typically drug-related and infrequent in the general population not exposed to drugs (e.g. Stevens-Johnson syndrome).
- An indication of dose-response (i.e. greater effect size if the dose is increased, smaller effect size if dose is reduced).

Arguments that may suggest that there is no reasonable possibility of a causal relationship could be:

- No plausible time to onset of the event relative to the time of drug exposure is evident (e.g. pre-treatment cases, diagnosis of cancer or chronic disease within days / weeks of drug administration; an allergic reaction weeks after discontinuation of the trial drug concerned).
- Continuation of the event despite the withdrawal of the medication, taking into account the pharmacological properties of the compound (e.g. after 5 half-lives). Of note, this criterion may not be applicable to events whose time course is prolonged despite removing the original trigger.
- There is an alternative explanation, e.g. situations where other drugs or underlying diseases appear to provide a more likely explanation for the observed event than the drug concerned.
- Disappearance of the event even though the trial drug treatment continues or remains unchanged.

5.2.6.2 Adverse event collection and reporting

5.2.6.2.1 AE Collection

The investigator shall maintain and keep detailed records of all AEs in the patient files.

The following must be collected and documented on the appropriate CRF(s) by the investigator:

- From signing the informed consent onwards until the individual patient's end of trial (= the End of Study (EoS) visit): all AEs (serious and non-serious) and all AESIs.
- After the individual patient's end of trial: the investigator does not need to actively monitor the patient for new AEs but should only report any occurrence of cancer and trial drug related SAEs and trial drug related AESIs of which the investigator may become aware of by any means of communication, e.g. phone call. Those AEs should be reported on the BI SAE form (see Section 5.2.6.1.2), but not on the CRF.

Vital Status Data Collection

Patients who discontinue the trial prematurely, who agree to be contacted further but do not agree to physical visits, should be followed up as described in Section 3.3.4.1, discontinuation of trial treatment. From then on until the individual patient's end of the trial the investigator must report any occurrence of cancer, report all deaths / fatal AEs regardless of relationship, and trial drug related SAEs and trial drug related AESIs the investigator becomes aware of as well as information on any AEs leading to hospitalization, whether related to trial drug or not.

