3.3.4.1 Discontinuation of Trial Treatment

In case the infusion or inhalation of study drug is permanenty discontinued before the whole amount of prepared solution has been administered to the patient, drug administration will not be re-initiated. Every effort should be made to keep the patient in the trial and perform all study procedures. If not possible, the patient will undergo the procedures at the Prematurely Discontinued before Day 29 or the Prematurely Discontinued after Day 29 visit (whichever is appropriate) and follow-up as outlined in the Flow Chart and Section 6.2.3. A phone contact at the end of the planned observation period should occur to collect the most relevant information: vital status (please see Section 5.2.6.1.1), outcome events, adverse events, or last contact date in case of lost to follow-up. The reason for interrupting trial treatment must be documented in the patient files and CRF.

If new efficacy / safety information becomes available, BI will review the benefit-riskassessment and, if needed, pause or discontinue the trial treatment for all patients or take any other appropriate action to guarantee the safety of the trial patients.

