4.2 OTHER TREATMENTS, EMERGENCY PROCEDURES, RESTRICTIONS

4.2.1 Other treatments and emergency procedures

Stable doses of concomitant therapies for chronic conditions, for which neither the condition nor the treatment are judged to exclude the patient from participation (see Section 3.3), are permissible. In case of adverse event in need of treatment, symptomatic therapy according to investigator judgement will be permitted.

Infusion reaction

In case of an acute infusion reaction, the infusion will be interrupted and not be re-initiated. For infusion reactions requiring medical intervention, rescue medication including, but not limited to, acetaminophen/paracetamol, antihistamines, glucocorticoids, and IV fluids must be available on site.

Inhalation reaction

In case of bronchial hyperresponsiveness (e.g., bronchospasm), bronchodilators and/or antiinflammatory medications may be provided by inhalation or intravenously as deemed clinically appropriate.

Rescue treatment

During the trial, if COVID-19 worsens, the patient can be treated with medications at the discretion of the investigator (refer to Restricted medication Table 4.2.2.1:1, footnote 2) as per local guidelines. Any additional investigational products related to COVID-19 could be given for COVID-19 disease worsening, after Day 2 at the discretion of the investigator but may require additional safety monitoring by the site.

All efforts should be made to inform the patient of the importance of completing the protocol specified visits (See Flow Chart) up to Visit 9. Patients refusing to complete the scheduled visits after the day of treatment should at least provide safety information by phone at the respective visits.

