AEs/SAEs collection shall be performed until Day 91 and at last visit in case patient discontinues the trial prematurely before completion Day 29.

If needed in the opinion of the investigator, after the EoS (End of Trial) visit additional visits may be scheduled for continued safety monitoring.

Abnormal assessments or lab values judged clinically relevant by the investigator will be monitored until they returned to a medically acceptable level.

Vital status information is to be collected for each patient that completes the EOS visit. In case patient discontinues the trial prematurely before their scheduled EOS visit, vital status information and information whether the patient has been hospitalized shall be collected at planned completion date of each individual patient. Any locally approved means of vital status information collection is accepted.

Early treatment discontinuation

In case the infusion or inhalation of study drug is permanenty discontinued before the whole amount of prepared solution has been administered to the patient, drug administration will not be re-initiated. Patients should be encouraged to follow all study procedures until their individual EOS visit. Given the patient's agreement, the patient will undergo the procedures for early treatment discontinuation (see Section 3.3.4.1) and follow up as outlined in the Flowchart (and Section 6.2.3).

Trial completion:

Trial completion is defined as a patient having reached the EOS visit. EOS visit will be at Week 12, Day 91.

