7.2.6 Safety analyses

Adverse events will be coded using the Medical Dictionary for Drug Regulatory Activities (MedDRA). Standard BI summary tables and listings will be produced. All adverse events with an onset between start of treatment and end of the REP, a period of 90 days after the last dose of trial medication, will be assigned to the on-treatment period for evaluation.

All treated patients will be included in the safety analysis. In general, safety analyses will be descriptive in nature and will be based on BI standards. No hypothesis testing is planned.

Statistical analysis and reporting of adverse events will concentrate on treatment-emergent adverse events, i.e. all adverse events occurring between start of treatment and end of the REP. Adverse events that start before first drug intake and deteriorate under treatment will also be considered as 'treatment-emergent'.

Frequency, severity (as graded according to DAIDS Table 5.2.6.1.5:1 [R21-0379]), and causal relationship of adverse events will be tabulated by system organ class and preferred term after coding according to the current version of the Medical Dictionary for Drug Regulatory Activities (MedDRA) at database lock.

Laboratory data will be analysed both quantitatively as well as qualitatively. The latter will be done via comparison of laboratory data to their reference ranges. Values outside the reference range as well as values defined as clinically relevant will be summarised. Treatment groups will be compared descriptively with regard to distribution parameters as well as with regard to frequency and percentage of patients with abnormal values or clinically relevant abnormal values.

Vital signs, physical examinations, or other safety-relevant data observed at screening, baseline, during the course of the trial and at the end-of-trial evaluation will be assessed with regard to possible changes compared to findings before start of treatment.

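### For patients who leave the trial early but can still be phoned, the protocol's adverse event collection rules conflict, and one omits some unrelated SAEs and AESIs and most non-serious AEs within the 90-day safety window.

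*Protocol*

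**What the plan says.** Protocol Section 5.2.6.2.1 opens with full collection, from consent "until the individual patient's end of trial (= the End of Study (EoS) visit): all AEs (serious and non-serious) and all AESIs". Its Vital Status Data Collection paragraph then treats separately patients who discontinue the trial early, "who agree to be contacted further but do not agree to physical visits, should be followed up as described in" Section 3.3.4.1. From that point to the end of the patient's trial period, the investigator must report any cancer, all deaths, and "trial drug related SAEs and trial drug related AESIs the investigator becomes aware of as well as information on any AEs leading to hospitalization". The sentence goes on to say that hospitalisation events count whether or not they are drug-related.

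Other sections give different rules for a patient in this position:

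- Section 3.3.4.1: "A phone contact at the end of the planned observation period should occur to collect the most relevant information". Adverse events are on its list, with no relatedness condition.
- Section 4.2.1: "Patients refusing to complete the scheduled visits after the day of treatment should at least provide safety information by phone at the respective visits". The preceding sentence concerns visits up to Visit 9, which is Day 29.
- Section 5.2.6.2.2: SAEs and AESIs go to the sponsor within 24 hours of awareness, with no relatedness condition.

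On the analysis side, protocol Section 7.2.6 includes all treated patients and concentrates on "all adverse events occurring between start of treatment and end of the REP", the REP being 90 days. SAP Sections 7.8 and 7.8.1 likewise use the treated set and assign events up to 90 days after drug intake to treatment.

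**The concern.** The reduced list makes the site's causality judgement a filter on what is collected. Causality is normally recorded about an event that has already been captured.

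That filter is weak in this trial. Every patient has COVID-19, investigators are blinded (Section 4.1.5.1), and Section 5.2.6.1.6 accepts underlying disease as an argument against a causal link. An alternative explanation is therefore nearly always available. Section 1.2.6 states that the product's safety profile has not been established.

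Two sites could follow different sections for identical patients and return different data. The DMC and the final tables would then see fewer events from these patients, who stay in the denominator as if followed in full for 90 days. Section 3.3.4 itself expects that motivation to attend may fall after a single dose.

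**Working it through.** No plan figure has to be reproduced. The check sets the passages side by side and adds simple day counts.

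**Step 1. Rules for a patient who has left the trial, refuses visits and can be phoned**

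| Protocol section | When | What | Limited by relatedness? |
|---|---|---|---|
| 5.2.6.2.1, general rule | Consent to EoS visit | All AEs and AESIs | No |
| 5.2.6.2.1, Vital Status paragraph | Discontinuation to end of trial, on awareness | Cancer, deaths, AEs leading to hospitalisation, related SAEs and AESIs | Yes, for the other SAEs and AESIs |
| 3.3.4.1 | One call at end of period | Vital status, outcome events, adverse events | No |
| 4.2.1 | By phone at the visits, to Visit 9 | Safety information | No |
| 5.2.6.2.2 | Within 24 hours of awareness | SAEs and AESIs | No |

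**Step 2. What the reduced list leaves out**

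- Unrelated SAEs that are non-fatal, are not cancer and did not lead to hospitalisation. Hospitalisation is itself a seriousness criterion (Section 5.2.6.1.2), so unrelated SAEs that are serious on that ground stay reportable.
- Unrelated AESIs that are non-fatal and did not lead to hospitalisation.
- Non-serious AEs, unless they are related AESIs, cancer, or led to hospitalisation.

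**Step 3. Is the reduced list simply an exception to the general rule?** It can be read that way against the first row. The conflict remains, because the paragraph refers these patients to Section 3.3.4.1, whose content is unrestricted, and because it also differs from Sections 4.2.1 and 5.2.6.2.2.

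**Step 4. Overlap with the safety window.** The window runs from Day 1 to Day 91: 91 − 1 = 90 days.

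- Reduced list from just after Day 1: up to 90 of 90 days affected.
- From Day 8: 91 − 8 = 83 days.
- From Day 29: 91 − 29 = 62 days.

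Neither document shortens the at-risk period for these patients.

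**Step 5. Contacts already required.** Section 4.2.1 covers Days 3, 4, 8, 11, 15, 22 and 29, which is 7 contacts. Section 3.3.4.1 adds one at the end of the period. 7 + 1 = 8, the number of follow-up visits in Section 6.2.3. Only the content rule needs aligning.

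**The case against.** The strongest reply is that the sections address different patients and can be layered. The reduced list applies only to those who discontinue the trial. A patient who merely cannot attend need not discontinue: flow chart footnote 2 allows every clinic visit except Visit 2 to be done at home or by phone, and full collection then continues. Section 4.2.1 may be meant for patients who refuse visits without leaving. For those who do leave, the reduced list could be what is reported in the interim, with everything else picked up at the Section 3.3.4.1 call.

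The first part stands and narrows the affected group. The layering does not remove the problem: the protocol never says the list is only an interim minimum, and it still conflicts with Section 5.2.6.2.2. A single call at the end would also depend on recall over as much as 90 days.

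Other parts of the reply also stand:

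- Section 6.2.3 reads "AEs/SAEs collection shall be performed until Day 91 and at last visit in case patient discontinues the trial prematurely before completion Day 29". This fits the premature-discontinuation visit in the flow chart and should not be counted as a further conflicting rule for phone follow-up.
- Potential severe DILI is a poor example. It is defined by laboratory values, and a patient who refuses visits has no scheduled blood draw.
- Infusion reactions mostly fall within hours of the single dose, before visits stop.

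**Conclusion.** The conflict is in the text and should be resolved, within limits. A reader might infer three stronger things that the documents do not support.

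- *That all unrelated SAEs and AESIs are dropped.* The paragraph requires investigators to "report all deaths / fatal AEs regardless of relationship, and trial drug related SAEs and trial drug related AESIs the investigator becomes aware of", and it also keeps any cancer and any AE leading to hospitalisation, whatever the cause. The loss is the set in Step 2.
- *That this is the narrowest rule in the protocol.* Section 3.3.4 and flow chart footnote 19 set a thinner floor: vital status and hospitalisation only.
- *That a large number of patients is affected.* The documents give no rate of discontinuation with continued phone contact. Section 7.5.2 expects few losses to follow-up, but that is a different group. For scale only, each assumed 1% of about 1300 Phase III patients is 0.01 × 1300 = 13 patients. The true number is probably small.

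The Phase III primary endpoint is not touched, because deaths and hospitalisations stay on the reduced list. The effect is confined to completeness of safety data, in analyses that are descriptive. The trial stopped with 5 patients randomised and the SAP covers Phase II only, so the effect on the actual report is minor. The point concerns the plan as written.

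**What to change.** Reconcile Sections 5.2.6.2.1, 3.3.4.1, 4.2.1 and 5.2.6.2.2 into one collection rule:

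- While a patient who has stopped visits accepts phone contact, record all AEs, SAEs and AESIs regardless of relationship at the contacts already required: the scheduled visit days to Day 29 (Section 4.2.1) and the end-of-period call at Day 91 (Section 3.3.4.1).
- Remove the relatedness restriction from the Vital Status Data Collection paragraph for these patients.
- Keep the reduced list only for information learned passively about patients who decline all contact.

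The cost is amendment wording and slightly more eCRF entry for a few patients. No contact is added beyond those the protocol already asks for. Phone follow-up will still not detect laboratory-defined events unless blood is drawn elsewhere.

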5.2.6.2.2 AE reporting to the sponsor and timelines

The investigator must report SAEs, AESIs, and non-serious AEs which are relevant for the reported SAE or AESI, on the BI SAE form to the sponsor's unique entry point within 24 hours of becoming aware of the event, the country specific process will be specified in the ISF. The

Boehringer Ingelheim		
BI Trial No.: 1487-0001		20 Apr 2021
c33563257-02	Clinical Trial Protocol	Page 72 of 127

same timeline applies if follow-up information becomes available. In specific occasions, the investigator could inform the sponsor upfront via telephone. This does not replace the requirement to complete the BI SAE form.

With receipt of any further information to these events, a follow-up SAE form has to be provided. For follow-up information the same rules and timeline apply as for initial information. All (S)AEs, including those persisting after individual patient's end of trial must be followed up until they have resolved, have been assessed as "chronic" or "stable", or no further information can be obtained.

5.2.6.2.3 Pregnancy

In rare cases, pregnancy might occur in a clinical trial. Once a patient has been enrolled in the clinical trial and has taken trial medication, the investigator must report any drug exposure during pregnancy in a trial participant immediately (within 24 hours) by means of Part A of the Pregnancy Monitoring Form to the sponsor's unique entry point.

Similarly, potential drug exposure during pregnancy must be reported if a partner of a male trial participant becomes pregnant. This requires written consent of the pregnant partner. Reporting and consenting must be in line with local regulations. The ISF will contain the trial specific information and consent for the pregnant partner.

The outcome of the pregnancy associated with the drug exposure during pregnancy must be followed up and reported to the sponsor's unique entry point on the Pregnancy Monitoring Form for Clinical Studies (Part B).

The ISF will contain the Pregnancy Monitoring Form for Clinical Studies (Part A and B).

As pregnancy itself is not to be reported as an AE, in the absence of an accompanying SAE and / or AESI, only the Pregnancy Monitoring Form for Clinical Studies and not the SAE form is to be completed. If there is an SAE and / or AESI associated with the pregnancy an SAE form must be completed in addition.
Proprietary confidential information © 2021 Boehringer Ingelheim International GmbH or one or more of its affiliated companies

Details on sample collection for BI 767551 characteristics, processing, handling, and shipment are provided in the Laboratory Manual.

5.4

Clinical Trial Protocol

20 Apr 2021 Page 74 of 127

Proprietary confidential information © 2021 Boehringer Ingelheim International GmbH or one or more of its affiliated companies

ASSESSMENT OF BIOMARKER(S)

Refer to Section 5.6.2 for other assessments.

33563257-02Clinical Trial ProtocolPage 75 of 12Proprietary confidential information © 2021 Boehringer Ingelheim International GmbH or one or more of its affiliated companies

